### 9.1.3 Definition of Adverse Drug Reaction

Those AEs for which the relationship to the investigational product is considered “Related” will be handled as adverse drug reactions (ADRs).

### 9.1.4 Actions to Be Taken When Adverse Events Occur

When an AE occurs, the investigator or sub-investigator will provide appropriate treatment, will report the AE to the sponsor if necessary, and to the extent possible will monitor progress until the subject recovers or the AE is resolved or relieved. If it appears unlikely from a medical perspective that the subject will recover, this will be

explained to the subject, and monitoring of the subject as a part of the clinical trial will be concluded (although the treatment for the AE will be continued). In addition, clinical trial follow-up will be terminated and the clinical trial will be concluded if the investigator or sub-investigator decides further follow-up is unnecessary for the AE because there is no relationship between the AE and the investigational product, or if the subject refuses further follow-up.

## **9.2 Actions to Be Taken When Serious Adverse Events Occur**

If a serious adverse event (SAE) occurs after obtaining the subject's written ICF and up to Visit 11, the investigator or sub-investigator will provide appropriate treatment for the subject and will report the event by phone or fax to the sponsor within 24 hours after becoming aware of the event. The investigator will promptly submit a detailed written report of the event to the sponsor. Written report of SAEs will be prepared and submitted to the head of the study site or to the Institutional Review Board (IRB), using the form and procedures specified by the study site. Detailed information regarding the procedures for reporting SAEs is provided separately, in the standard operating procedures for SAEs.

In addition, the following types of events should be reported to the sponsor within 24 hours after becoming aware of the event by phone or FAX:

- Increase in ALT or AST  $\geq 5 \times$  ULN
- ALT or AST rises to  $\geq 3 \times$  ULN and persists for more than 2 weeks
- Concurrent increases in ALT or AST  $\geq 3 \times$  ULN and T-Bil  $\geq 2 \times$  ULN
- ALT or AST  $\geq 3 \times$  ULN associated with a clinical presentation suggestive of liver injury (ie, including the appearance of fatigue, nausea, vomiting, jaundice, right upper quadrant pain or tenderness, fever, rash, and/or eosinophilia)
- AE related to suicide (if there are any "yes" responses to any of the questions in the C-SSRS)

The following types of events should be reported to the sponsor as promptly as possible after becoming aware of the event by phone or FAX.

- Severe hepatobiliary AE
- Hepatobiliary AE leading to discontinuation

- Any transaminase elevation associated with a clinical presentation suggestive of liver injury
- An elevation of ALT or AST  $\geq 3 \times$  ULN (without clinical presentation suggestive of liver injury)

### **9.3 Exposure In Utero During Clinical Studies**

Daiichi Sankyo must be notified of any subject who becomes pregnant while receiving or at the time of discontinuing the investigational product. All pregnancies must be followed to conclusion to determine their outcome. This information is important for both drug safety and public health concerns. It is the responsibility of the investigator to report any pregnancy in a subject using the Exposure In Utero (EIU) Reporting form. The investigator will contact the study monitor to obtain the EIU Reporting Form upon learning of a pregnancy. If the outcome of the pregnancy meets the criteria for immediate classification as a SAE (ie, post-partum complications, spontaneous abortion, stillbirth, neonatal death, or congenital anomaly, including congenital anomaly in an aborted fetus), the investigator should follow the procedures for reporting SAEs.

### **9.4 Clinical Laboratory Evaluations**

The study site staff will collect blood and urine specimens for routine laboratory tests at specified times. Specimens will be stored under conditions stipulated in the Sample Handling Manual until they are transported for measurement. Specimens will be transported and measured by a central laboratory. Table 9-2 summarizes the laboratory parameters to be assessed and the times of assessment.

Results of all laboratory tests will be reported from the central laboratory to the site.

A value or finding that represents a clinically significant abnormal change should be regarded as an AE, and should be described (diagnosed) appropriately in the CRF.

Table 9-2: Laboratory Parameters to be Assessed, and Time of Assessment

	Parameters	Time of assessment
Hematology	WBC, RBC, hemoglobin, hematocrit, platelet count, differential leukocyte (neutrophil, eosinophil, basophil, monocyte, lymphocyte) counts, reticulocyte count	
Blood chemistry	Total protein, albumin, A/G ratio, T-Bil, AST (GOT), ALT (GPT), ALP, $\gamma$ -GT ( $\gamma$ -GTP), LDH, BUN, creatinine, uric acid, creatine kinase, total cholesterol, triglycerides, Na, K, Cl, Ca, Mg, inorganic phosphorus, bicarbonate, CRP	Visit 1, Visit 2, Visit 3, Visit 4, Visit 5, Visit 6, Visit 7, Visit 8, Visit 9, Visit 10, and Visit 11
Urinalysis	Standard urinalysis, including microscopic examination	
Pregnancy	Qualitative test (urine)	Visit 1 and Visit 10
HbA1c (only in patients with DPNP)	HbA1c	Visit 1, Visit 6, and Visit 10
Fasting blood glucose (only in patients with DPNP)	Fasting blood glucose level	Visit 1, Visit 6, and Visit 10

A/G ratio = albumin/globulin ratio CRP = C-reactive protein, LDH = lactate dehydrogenase, RBC = red blood cell, WBC = white blood cell

As described in Section 4.2.1, increases in aminotransferases have been observed in the DS-5565 development program to date. Special monitoring of such elevations during Phase 3 is described below. The Hepatic Adjudication Committee (HAC) charter includes a process by which selected cases will be adjudicated by a liver disease specialist (Section 11.10). In cases of liver laboratory abnormalities, it is important to

ensure that the nature and the extent of liver injury is identified and study subjects are monitored until the liver laboratory assessments return to normal. Subjects who have any transaminase elevation associated with a clinical presentation suggestive of liver injury (ie, including the appearance of fatigue, nausea, vomiting, jaundice, right upper quadrant pain or tenderness, fever, rash, and/or eosinophilia) or an elevation of ALT or AST  $\geq 3 \times$  ULN (without clinical presentation suggestive of liver injury) at any visit should be monitored closely, according to the following:

- Repeat liver tests of at least all 4 of the usual serum measures (ALT, AST, alkaline phosphatase [ALP], and T-Bil) at least 2 times weekly (the first repeat should be within 48 to 72 hours of initial abnormality) until values have decreased to  $< 2 \times$  ULN, then at least every 1 or 2 weeks until resolution or return to baseline. An additional serum separating tube of blood will be collected at time of event and until values return to baseline. Samples will be stored for further analysis, as required.
- Review or obtain a detailed history of symptoms and prior or concurrent diseases.
- Review or obtain a history of the use of concomitant drugs, including nonprescription medications, herbal and dietary supplements, alcohol, recreational drugs, special diets, and exposure to environmental chemical agents..
- Rule out alcoholic hepatitis; Nonalcoholic steatohepatitis; hypoxic/ischemic hepatopathy; and biliary tract disease.
- Perform additional liver function tests (LFTs) (eg, serum lactate dehydrogenase [LDH], ALP, gamma-glutamyl transpeptidase, prothrombin time), evaluations for potential viral etiologies (including hepatitis A, B, C, E; cytomegalovirus; EBV) and autoimmune etiologies (anti-nuclear antibody, anti-smooth muscle antibody, anti-mitochondrial antibody).

[figure not shown]
Combined elevations of aminotransferases and bilirubin meeting the criteria of a potential Hy's Law case [ALT or AST  $\geq 3 \times$  ULN with simultaneous T-Bil  $\geq 2 \times$  ULN], either serious or non-serious and whether or not causally related, should always be reported to the sponsor within 24 hours (refer to Section 9.2), with the investigator's assessment of seriousness, causality, and a detailed narrative. (Food Drug Administration [FDA]'s Guidance for Industry: Drug-Induced Liver Injury: Premarketing Clinical Evaluation; July 2009; <http://www.fda.gov/downloads/Drugs/Guidance/UCM174090.>). These events should

be reported as soon as possible following the procedures outlined in Section 9.2 for SAE reporting. The sponsor will be responsible for reporting the case(s) to the FDA.

Criteria for discontinuing subjects based on transaminase increases are provided in Section 4.2.1.

For subjects discontinued from the study due to any transaminase increase or hepatic event, the following should be performed:

- Gastroenterology or hepatology consultation
- Hepatobiliary ultrasound

a: ie, including the appearance of fatigue, nausea, vomiting, jaundice, right upper quadrant pain or tenderness, fever, rash, and/or eosinophilia

b: Evaluations for potential viral etiologies will include: Hep A Ab by IgM acute, HBsAg, HBeAg, anti-HBc, Hep C RNA by PCR, Hep E IgG Ab, Hep E IgM Ab, EBV IgG Ab, EBV IgM Ab, and CMV DNA by PCR

Abbreviations: ALP = alkaline phosphatase, ALT = alanine aminotransferase, AST = aspartate aminotransferase; CMV = cytomegalovirus, EBV = Epstein-Barr virus, γ-GT = gammaglutamyltransferase, LDH = lactate dehydrogenase, LFT = liver function test, PT = prothrombin time, ULN = upper limit of normal

## **9.5 Vital Sign**

Vital sign will be recorded at all visits and will include supine pulse rate and supine and orthostatic blood pressure. For measurement of supine blood pressure, subjects should be in a supine or semirecumbent position for at least 5 minutes before the blood pressure measurement. Measurement of orthostatic blood pressure should follow measurement of supine blood pressure. Subjects should be asked to stand for 3 minutes before measurement of orthostatic blood pressure. Measurement of blood pressure should be conducted using a calibrated manometer or automatic inflatable cuff monitor; the blood pressure cuff should be kept in place between supine and orthostatic blood pressure measurements. Results will be recorded in the CRF.

## **9.6 Electrocardiograms**

At the stipulated times (Visit 1 and Visit 10), 12-lead ECG will be performed. Results (Normal/Abnormal, not clinically significant/Abnormal, clinically significant) will be recorded in the CRF.

## **9.7 Physical Findings**

### **9.7.1 Body Height and Weight**

At Screening (Visit 1), body height will be measured. Body weight will be measured at each visit. Results will be recorded in the CRF.

### **9.7.2 Physical Examinations**

At Screening Visit (Visit 1) and End of Treatment/Early Termination Visit (Visit 10), a complete physical examination, with the exception of pelvis, breast, and rectum in women and the genitourinary system and prostate in men, will be performed on each subject.

At Visit 2, Visit 3, Visit 4, Visit 5, Visit 6, Visit 7, Visit 8, Visit 9, and Visit 11, the examination should minimally include clinical evaluations of the head, neck, thyroid, eyes, ears, nose, throat, heart, lungs, lymph nodes, abdomen, skin, extremities, and musculoskeletal system.

Results will be recorded in the CRF.

### **9.7.3 Evaluation of Edema**

At Screening Visit (Visit 1) and Visit 10, evaluation of edema will be performed including physical examination and/or pitting. Results (presence or absence of edema and expression site) will be recorded in the CRF.

## **9.8 Other Safety Assessments**

### **9.8.1 Neurological Examination for Patients with DPNP**

This assessment will be performed only in patients with DPNP.

A full neurological examination will be performed at the stipulated times (Visit 1 and Visit 10). An abbreviated examination will be performed at Visit 2, Visit 3, Visit 4, Visit 5, Visit 6, Visit 7, Visit 8, Visit 9, and Visit 11.

The full neurological examination will include the following: ankle jerk, vibratory sensation, pain sensation including hyperalgesia, allodynia, muscle strength (0-to-5 rating; ankle dorsiflexion), and gait/station (observation of regular walking, heel-to-toe [tandem] walking, and Romberg test, each assessed as normal or abnormal). The tests of ankle jerk, vibratory sensation, and pain sensation are detailed in the Procedures manual for the Diagnosis of Diabetic Peripheral Neuropathy and Neurological Examination. The assessment on pain symptom will be recorded as “Pain excepting tingling and pins & needles”, “Tingling or pins & needles” or “Dysesthesia”.

The abbreviated examination will include muscle strength and gait/station based on physical examination and medical interview, each assessed as normal or abnormal.

Results will be recorded in the CRF.

### **9.8.2 Neurological Examination for Patients with PHN**

This assessment will be performed only in patients with PHN.

A full neurological examination will be performed at the stipulated times (Visit 2 and Visit 10). An abbreviated examination will be performed at Visit 2, Visit 3, Visit 4, Visit 5, Visit 6, Visit 7, Visit 8, Visit 9, Visit 10 and Visit 11.

The full neurological examination will include the following: muscle strength (0-to-5 rating; ankle dorsiflexion), and gait/station (observation of regular walking, heel-to-toe [tandem] walking, and Romberg test, each assessed as normal or abnormal). The tests of the neurological examination are detailed in the Procedures manual for the Neurological Examination.

The abbreviated examination will include muscle strength and gait/station based on physical examination and medical interview, each assessed as normal or abnormal.

Results will be recorded in the CRF.

### **9.8.3 Ophthalmologic Examination**

The ophthalmologic examination will be performed at Visit 1 (allowed to Visit 2) and Visit 10 (allowed to 4 days after). The examination includes examination of visual acuity and funduscopic examination. For a given subject, visual acuity should be examined under the same conditions (uncorrected or corrected) at both visits, and funduscopy should be performed with the same device. Results of visual acuity will be recorded as values, and results of funduscopic examination will be recorded as [Normal/Abnormal, not clinically significant/Abnormal, clinically significant] in the CRF.

### **9.8.4 Columbia-Suicide Severity Rating Scale**

The C-SSRS is a tool designed to systematically assess and track suicidal AEs (behavior and ideation). The C-SSRS assesses lifetime suicidality during an initial baseline evaluation using standardized questions, and then prospectively monitors ideations and behaviors at subsequent follow-up assessments throughout the trial. The reviewer is an investigator or sub-investigator who has completed training prior to the study using the training DVD. The C-SSRS will be administered by the investigator or sub-investigator at each visit. Answers to all relevant questions will be recorded in the CRF. If the subject is judged to have suicidal behavior and/or suicidal ideation, appropriate measures will be implemented such as referring the subject to a specialist as described in the withdrawal procedures (see Section 4.2.3).

### **9.8.5 Hospital Anxiety and Depression Scale**

At each visit, subjects will provide a self-assessment using the HADS. The HADS consists of 7 items to score depression (4-point scale) and 7 items to score anxiety (4-point scale). The subject will respond to each item on the questionnaire. Based on the results, the investigator will check for the presence or absence of depression and/or anxiety. If the subject is judged to have an AE, appropriate measures will be implemented such as referring the subject to a specialist. Results will be recorded in the CRF.

### **9.8.6 Pregnancy test**

Pregnancy tests (urine tests) will be conducted at the stipulated times (Visit 1 and Visit 10), for women of child-bearing potential only. All female subjects will be considered as women of child-bearing potential unless they have undergone surgical sterilization (with documented bilateral oophorectomy) or are postmenopausal and have

experienced no menses within the previous 6 months. The subject is considered to be postmenopausal when 12 consecutive months of absence of menstruation is confirmed with no pathological or physiological factors. Results will be recorded in the CRF.

## **10. OTHER ASSESSMENTS**

No other assessments will be performed.

## **11. STATISTICAL METHODS**

### **11.1 Objective**

The primary objective is to characterise the safety and tolerability of DS-5565 in subjects with moderate to severe renal impairment. The secondary objectives including the efficacy are shown in section 2.1.2.

### **11.2 General Statistical Considerations**

The statistical package SAS® (Version 9.2 or higher) will be used to produce tables, figures, and listings.

Safety analysis set will be used for all safety and efficacy analyses and PK analysis set will be for all PK analyses. All analyses will be conducted by CrCL group (ie, moderate and severe renal function impaired patients group).

Missing weekly ADPS value will be imputed based on "nonfuture dependence" model using the pattern mixture approach under the missing not at random (MNAR) mechanism so that bad outcomes (greater weekly ADPS value) can be attributed to subjects who discontinued the trial before Week 14. Detail will be at Section 11.5.2.1 and in the SAP.

Raw data will be presented to the exact precision at which they were collected. For summary statistics, means and medians will be displayed to one more decimal place than was determined for raw data, dispersion statistics will have two more decimal places, and the minimum and maximum will be displayed to the same number of decimal places as the raw data.

Quantitative data will be tabulated with descriptive summary statistics: arithmetic mean, standard deviation (SD), median, minimum and maximum values, and number of observations. For categorical data, frequency tables will be provided.

Analysis for the change from baseline, including the shift table, will be conducted for the subjects who have an available baseline value and at least 1 post-randomization value.

PK analysis will be detailed in the PK analysis plan (PAP).

A detailed SAP and PAP describing the methodology to be used in the final analysis will be prepared before data unblinding. A change in the planned statistical analysis will require a protocol amendment only if it substantively alters the principal features of the protocol. Any deviations from the planned statistical analyses in the protocol will be fully described in the SAP and PAP.

### **11.3 Analysis Sets**

The safety analysis set will include all subjects who signed the ICF and received at least 1 dose of study medication.

The PK analysis set will include all subjects who signed the ICF and received a dose of DS-5565 and had at least 1 PK sample collected.

### **11.4 Study Population Data**

Demographic and baseline characteristics will be summarized for the safety and PK analysis sets.

### **11.5 Efficacy Analyses**

#### **11.5.1 Primary Efficacy Analyses**

Not applicable.

#### **11.5.2 Secondary Efficacy Analyses**

All efficacy analyses will be performed using the safety analysis set. The summary statistics and/or frequency tables will be provided by CrCL group at each week or scheduled visit. No hypothesis testing will be conducted for all efficacy endpoints.

##### **11.5.2.1 Average Daily Pain Score**

Observed weekly ADPS and change from baseline will be summarized by CrCL group and week.

Missing weekly ADPS values will be imputed based on a multiple imputation (MI) method using “nonfuture dependence” model which is specified by the pattern mixture approach with shifting parameters under MNAR mechanism. The imputation method above will consider the reason for dropout together with the time of dropout for constructing the missing data pattern.

The statistical model used for the MI data generation will be the Markov Chain Monte Carlo method with adjustment for covariates (eg, age, sex) to produce a monotone pattern first, and then the imputation will continue using the Regression with Predictive Mean Matching method for the monotone pattern with the same set of covariates. The primary shifting parameter values corresponding to the three categories in the pattern mixture model will be chosen as (1.0, 1.0, 0.5) for dropouts due to AE, LOE and AOR, respectively, and the corresponding shifting amount of the weekly ADPS imputed at first missing week is given by  $(1.0, 1.0, 0.5) * RSD * U(0,1)$  where  $U(0,1)$  is a random variable

from a uniform distribution with a range of 0 to 1, and RSD is the residual SD at first missing week after imputation. The imputed value will be replaced with 10 (the maximal ADPS score) when the imputed value of ADPS score is over 10. Additionally, for dropouts due to LOE, the imputed values will be bound so that a subject's imputed weekly ADPS after discontinuation cannot be better than that subject's baseline ADPS. Each complete imputed dataset will be analyzed using the repeated measures analysis with week as the fixed effect, week as the repeated effect, and baseline ADPS as a covariate to provide LS mean in weekly ADPS at each week. The results of the analysis from each complete imputed dataset will be combined using Rubin's rule.

Sensitivity analyses will include following:

- Repeated measures analysis using observed data only
- ANCOVA using Baseline Observation Carried Forward
- ANCOVA using LOCF

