### **3. STUDY DESIGN**

#### **3.1 Overall Plan**

##### **3.1.1 Study Type**

This is an open-label study for treatment of DPNP or PHN in subjects with moderate to severe renal impairment.

Study sites: Approximately 35 study sites in Japan.

Planned sample size: Approximately 35 subjects will be enrolled in the study.

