### **11.11 Sample Size Determination**

Approximately 35 subjects with moderate and severe renal dysfunction will be enrolled in the study.

We need 30 subjects to observe at least 1 AE of moderate/severe dizziness and somnolence with 95% probability if the event rate is assumed to be 10%, which is nearly double of observed proportion in the Asian DPNP Phase 2 study (DS5565-A-J202).

Considering dropout, total of approximately 35 subjects will be enrolled into the study.

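### Does leaving the grouping, week history and covariates of the ADPS imputation open make it unworkable with about 35 subjects?

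*Combined protocol and SAP*

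**What the plan says.** Section 11.5.2.1 gives the first imputation step as a "Markov Chain Monte Carlo method with adjustment for covariates (eg, age, sex) to produce a monotone pattern first". The second step is regression with predictive mean matching on the same covariates. Values at the first missing week are then shifted upward by 1.0 (adverse event or lack of efficacy) or 0.5 (the third category) times a uniform random number times RSD, where "RSD is the residual SD at first missing week after imputation".

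On grouping, Section 11.2 has a general rule: "All analyses will be conducted by CrCL group (ie, moderate and severe renal function impaired patients group". On the missing-data method it says "Detail will be at Section 11.5.2.1 and in the SAP". On timing it says "A detailed SAP and PAP describing the methodology to be used in the final analysis will be prepared before data unblinding".

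Section 11.11 states that "Approximately 35 subjects with moderate and severe renal dysfunction will be enrolled in the study", with no split between the groups. Section 11.5.2 states that "No hypothesis testing will be conducted for all efficacy endpoints". The text supplied contains the protocol only; no separate SAP text is in it.

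**The concern.** Three choices that define an imputation model are open: grouping, number of earlier weeks, and covariates (the list is only illustrative). The general rule in Section 11.2 suggests imputing by CrCL group. So does the repeated measures model in Section 11.5.2.1, which has no CrCL term and must be fitted separately to give group means.

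With about 35 subjects in total, by-group imputation on the full weekly history asks more of the smaller group than it can supply. If the regression leaves no residual degrees of freedom, RSD is undefined under one reading of its definition, and RSD scales the penalty for dropping out.

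The timing wording adds to the worry. Section 3.1.1 says "This is an open-label study for treatment of DPNP or PHN in subjects with moderate to severe renal impairment", so there is no unblinding before which the SAP must be finished. Taken together, the imputation model might be repaired after the results are visible. At stake are the Week 14 means for ADPS and any responder rate computed from imputed values.

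**Working it through.** **Inputs.** Section 11.11: 30 subjects needed, about 35 enrolled. Section 6.3: 14 weeks of treatment, so 14 weekly scores. Section 11.5.2.1: age and sex named as covariates. The split by group is not stated, but the smaller group of 35 has at most 17.

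**The plan's own figure.** The chance of at least one event at a 10% rate is 1 − 0.9^n: 0.948 at n = 28, 0.953 at 29, 0.958 at 30. The stated 30 is sound. Going from 30 to 35 implies dropout of 5/35 = 14.3%.

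**Step 1: first step run by group, all weeks.** The rank of a sample covariance matrix of p variables is at most min(n − 1, p).

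| Variables | p | Short by, n = 17 | n = 15 | n = 10 | n = 5 |
|---|---|---|---|---|---|
| 14 weeks, age, sex | 16 | 0 | 2 | 7 | 12 |
| plus baseline ADPS | 17 | 1 | 3 | 8 | 13 |

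With only the covariates that Section 11.5.2.1 names for imputation, the model has full rank at n = 17. The shortfall at 17 appears only if baseline ADPS is added, and the section names baseline only for the later repeated measures model. Smaller groups fall short either way.

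**Step 2: second step run by group, all earlier weeks.** At Week 14 there are 1 + 2 + 13 = 16 coefficients (17 with baseline). One dropout among 17 leaves 16 observed, so residual df = 0 (or −1). With baseline included, Week j has j + 3 coefficients. After one dropout, the first week with no residual df is Week 13, 11, 6 or 1 for n = 17, 15, 10 or 5, so k = 2, 4, 9 or 14 weeks are affected. Assume 14.3% dropout spread evenly over 14 weeks. The chance that someone's first missing week falls there is 1 − (1 − (5/35)·k/14)^n = 30%, 46%, 62% and 54%. These figures hold only for full history with baseline, and only if RSD comes from that regression.

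**Step 3: other readings of the same text.**

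- Pooled; CrCL group, age, sex, baseline and all 13 earlier weeks: 18 coefficients, 30 − 18 = 12 df.
- Pooled; CrCL group, age, sex, baseline and two earlier weeks: 7 coefficients, 30 − 7 = 23 df.
- By group; age, sex, baseline and one earlier week: 5 coefficients, so 5 df with 10 observed and 10 df with 15 observed.
- By group; age, sex, baseline and two earlier weeks: 6 coefficients, so 3 df in a group of 10 with one dropout, and 0 in a group of 7 with one dropout.

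All but the last case at n = 7 or fewer can be fitted.

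**Step 4: size of the effect.**

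*Pooling with CrCL left out.* If earlier weeks carried no information, a dropout's imputed value would be drawn toward the pooled mean. The smaller group's mean would then move by (dropout share) × (other group's share) × (true difference). For the difference, take the whole span of mean changes across DS-5565 doses in Section 1.1.1.5.3, −2.0 to −2.8, or 0.8 points. At 25:10 this is 0.143 × 25/35 × 0.8 = 0.08 points. At twice the dropout in both groups it is 0.16. Weekly history reduces it: simulations with five random dropouts gave 0.037 to 0.062 per point of difference, or 0.03 to 0.05 at 0.8 points. They depend on a within-subject correlation that the documents do not give, so the bound is the firmer figure.

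*By group with few df.* The 95% range of an estimated RSD relative to its true value is the square root of (chi-square quantile/df): 0.27 to 1.77 at 3 df, and 0.71 to 1.29 at 23 df. A dropout for an adverse event or lack of efficacy is shifted by 0.5 × RSD on average. One such dropout in 10 moves the group mean by 0.5/10 = 0.05 × RSD, if the shift carries through to Week 14 in full. An error factor of 1.77 adds 0.05 × 0.77 = 0.04 points per point of true RSD.

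**The case for a change.** The strongest argument for a change is that by-group imputation is the natural reading, that the smaller group may well be far below 17, and that two or three sentences would close the gap at no cost. The section fixes the shift sizes, the cap at 10 and the bound for lack of efficacy, so silence on grouping and history stands out. With no usable date for the SAP, the repair could follow sight of the data.

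Part of this stands. The omissions are real, and by-group imputation on the full history cannot be run at this sample size once the smaller group has a dropout.

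The rest does not carry. The general rule concerns analyses, and imputation prepares data for them. The rule is not applied literally elsewhere either, since Section 11.7.1 also tabulates all treated subjects together. Section 11.5.2.1 attaches CrCL group to the observed summaries and not to the imputation. Using every week is an assumption that the text does not make. RSD after imputation may also mean a residual SD from the completed data, with a different df count.

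The remedy is not clear-cut. Pooling assumes common slopes and a common residual SD in the two groups; separate fits avoid that but rest on very few df.

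The unblinding phrase looks carried over from a randomized-trial template. Section 11.2 also speaks of post-randomization values and Section 4.2.2 of withdrawal before randomization, in a study that has neither randomization nor blinding. Correcting the phrase would change no result.

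**Conclusion.** No change to the plan follows. This is missing detail that Section 11.2 leaves to the SAP, together with a slip in the wording on timing. The one unworkable reading would show itself as a singular fit, and the ordinary responses (pool the groups, or shorten the history) agree with what is written.

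The numerical stake is small: a bound of about 0.08 points at a 25:10 split, likely 0.03 to 0.05, if CrCL is left out of a pooled model, and about 0.04 points per point of RSD if a group of 10 is imputed alone with a short history. The first effect vanishes if the groups do not differ, and Section 3.2.1 chose the two regimens to give equivalent exposure. ADPS is a secondary endpoint with no test attached. The observed-data, baseline-carried-forward and LOCF analyses do not use the imputation model, and the primary safety objective is untouched.

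The conclusion assumes about 35 enrolled, dropout near the 14% implied by Section 11.11 and similar in both groups, and a difference between groups no larger than 0.8 points. The SAP itself was not available to check.
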